13.3.18 Progression-free survival

Usually in all Oncology studies, patients are followed for tumor progression after discontinuation of study medication for reasons other than progression or death. If this is not used, e.g. in Phase I or II studies, this should be clearly stated in the protocol. Note that randomized trials (preferably blinded) are recommended where PFS is to be the primary endpoint.

Progression-free survival (PFS) is the time from date of randomization/start of treatment to the date of event defined as the first documented progression or death due to any cause. If a patient has not had an event, progression-free survival is censored at the date of last adequate tumor assessment.

13.3.19 Overall survival

All patients should be followed until death or until patient has had adequate follow-up time as specified in the protocol whichever comes first. The follow-up data should contain the date the patient was last seen alive / last known date patient alive, the date of death and the reason of death (“Study indication” or “Other”).

Overall survival (OS) is defined as the time from date of randomization/start of treatment to date of death due to any cause. If a patient is not known to have died, survival will be censored at the date of last known date patient alive.

13.3.20 Time to progression

Some studies might consider only death related to underlying cancer as an event which indicates progression. In this case the variable “Time to progression” might be used. TTP is defined as PFS except for death unrelated to underlying cancer.

Time to progression (TTP) is the time from date of randomization/start of treatment to the date of event defined as the first documented progression or death due to underlying cancer. If a patient has not had an event, time to progression is censored at the date of last adequate tumor assessment.

13.3.21 Time to treatment failure

This endpoint is often appropriate in studies of advanced disease where early discontinuation is typically related to intolerance of the study drug. In some protocols, time to treatment failure may be considered as a sensitivity analysis for time to progression. The list of discontinuation reasons to be considered or not as treatment failure may be adapted according to the specificities of the study or the disease.

Time to treatment failure (TTF) is the time from date of randomization/start of treatment to the earliest of date of progression, date of death due to any cause, or date of discontinuation due to reasons other than ‘Protocol violation’ or ‘Administrative problems’. The time to treatment failure for patients who did not experience treatment failure will be censored at last adequate tumor assessment.

13.3.22 Duration of response

The analysis of the following variables should be performed with much caution when restricted to responders since treatment bias could have been introduced. There have been reports where a treatment with a significantly higher response rate had a significantly shorter duration of response but where this probably primarily reflected selection bias which is explained as follows: It is postulated that there are two groups of patients: a good risk group and a poor risk group. Good risk patients tend to get into response readily (and relatively quickly) and tend to remain in response after they have a response. Poor risk patients tend to be difficult to achieve a response, may have a longer time to respond, and tend to relapse quickly when they do respond. Potent agents induce a response in both good risk and poor risk patients. Less potent agents induce a response mainly in good risk patients only. This is described in more detail by Morgan (1988).

It is recommended that an analysis of all patients (both responders and non-responders) be performed whether or not a “responders only” descriptive analysis is presented. An analysis of responders should only be performed to provide descriptive statistics and even then interpreted with caution by evaluating the results in the context of the observed response rates. If an inferential comparison between treatments is required this should only be performed on all patients (i.e. not restricting to “responders” only) using appropriate statistical methods such as the techniques described in Ellis et al (2008). It should also be stated in the protocol if duration of response is to be calculated in addition for unconfirmed response.

For summary statistics on “responders” only the following definitions are appropriate. (Specific definitions for an all-patient analysis of these endpoints are not appropriate since the status of patients throughout the study is usually taken into account in the analysis).

Duration of overall response (CR or PR): For patients with a CR or PR (which may have to be confirmed the start date is the date of first documented response (CR or PR) and the end date and censoring is defined the same as that for time to progression.

The following two durations might be calculated in addition for a large Phase III study in which a reasonable number of responders is seen.

Duration of overall complete response (CR): For patients with a CR (which may have to be confirmed) the start date is the date of first documented CR and the end date and censoring is defined the same as that for time to progression.

Duration of stable disease (CR/PR/SD): For patients with a CR or PR (which may have to be confirmed) or SD the start and end date as well as censoring is defined the same as that for time to progression.

13.3.23 Time to response

Time to overall response (CR or PR) is the time between date of randomization/start of treatment until first documented response (CR or PR). The response may need to be confirmed depending on the type of study and its importance. Where the response needs to be confirmed then time to response is the time to the first CR or PR observed.

Although an analysis on the full population is preferred a descriptive analysis may be performed on the “responders” subset only, in which case the results should be interpreted with caution and in the context of the overall response rates, since the same kind of selection bias may be introduced as described for duration of response in Section 13.3.22. It is recommended that an analysis of all patients (both responders and non-responders) be performed whether or not a “responders only” descriptive analysis is presented. Where an inferential statistical comparison is required, then all patients should definitely be included in the analysis to ensure the statistical test is valid. For analysis including all patients, patients who did not achieve a response (which may have to be a confirmed response) will be censored using one of the following options.

- at maximum follow-up (i.e. FPFV to LPLV used for the analysis) for patients who had a PFS event (i.e. progressed or died due to any cause). In this case the PFS event is the worst possible outcome as it means the patient cannot subsequently respond. Since the statistical analysis usually makes use of the ranking of times to response it is sufficient to assign the worst possible censoring time which could be observed in the study which is equal to the maximum follow-up time (i.e. time from FPFV to LPLV)
- at last adequate tumor assessment date otherwise. In this case patients have not yet progressed so they theoretically still have a chance of responding

Time to overall complete response (CR) is the time between dates of randomization/start of treatment until first documented CR. Similar analysis considerations including (if appropriate) censoring rules apply for this endpoint described for the time to overall response endpoint.

13.3.24 Definition of start and end dates for time to event variables

Assessment date

For each assessment (i.e. evaluation number), the **assessment date** is calculated as the latest of all measurement dates (e.g. X-ray, CT-scan) if the overall lesion response at that assessment is CR/PR/SD/UNK. Otherwise - if overall lesion response is progression - the assessment date is calculated as the earliest date of all measurement dates at that evaluation number.

Start dates

For all “time to event” variables, other than duration of response, the randomization/ date of treatment start will be used as the start date.

For the calculation of duration of response the following start date should be used:

- Date of first documented response is the assessment date of the first overall lesion response of CR (for duration of overall complete response) or CR / PR (for duration of overall response) respectively, when this status is later confirmed.

End dates

The end dates which are used to calculate ‘time to event’ variables are defined as follows:

- Date of death (during treatment as recorded on the treatment completion page or during follow-up as recorded on the study evaluation completion page or the survival follow-up page).
- Date of progression is the first assessment date at which the overall lesion response was recorded as progressive disease.
- Date of last adequate tumor assessment is the date the last tumor assessment with overall lesion response of CR, PR or SD which was made before an event or a censoring reason occurred. In this case the last tumor evaluation date at that assessment is used. If no postbaseline assessments are available (before an event or a censoring reason occurred) the date of randomization/start of treatment is used.
- Date of next scheduled assessment is the date of the last adequate tumor assessment plus the protocol specified time interval for assessments. This date may be used if back-dating is considered when the event occurred beyond the acceptable time window for the next tumor assessment as per protocol (see Section 13.3.25).

Example (if protocol defined schedule of assessments is 3 months): tumor assessments at baseline - 3 months - 6 months - missing - missing - PD. Date of next scheduled assessment would then correspond to 9 months.

- Date of discontinuation is the date of the end of treatment visit.
- Date of last contact is defined as the last date the patient was known to be alive. This corresponds to the latest date for either the visit date, lab sample date or tumor assessment date. If available, the last known date patient alive from the survival follow-up page is used. If no survival follow-up is available, the date of discontinuation is used as last contact date.
- Date of secondary anti-cancer therapy is defined as the start date of any additional (secondary) antineoplastic therapy or surgery.

13.3.25 Handling of patients with non-measurable disease only at baseline

It is possible that patients with only non-measurable disease present at baseline are entered into the study, either because of a protocol violation or by design (e.g. in Phase III studies with PFS as the primary endpoint). In such cases the handling of the response data requires special consideration with respect to inclusion in any analysis of endpoints based on the overall response evaluations.

It is recommended that any patients with only non-measurable disease at baseline should be included in the main (ITT) analysis of each of these endpoints.

Although the text of the definitions described in the previous sections primarily relates to patients with measurable disease at baseline, patients without measurable disease should also be incorporated in an appropriate manner. The overall response for patients with measurable disease is derived slightly differently according to Table 15.

Table 15: Overall lesion response at each assessment: patients with non-target disease only

Non-target lesions	New Lesions	Overall lesion response
CR	No	CR
Non-CR/Non-PD ¹	No	Non-CR/non-PD
UNK	No	UNK
PD	Yes or No	PD
Any	Yes	PD

¹ As defined in Section 13.3.8.

In general, the **non-CR/non-PD response** for these patients is considered equivalent to an SD response in endpoint determination. In summary tables for best overall response patients with only non-measurable disease may be highlighted in an appropriate fashion e.g. in particular by displaying the specific numbers with the non-CR/non-PD category.

In considering how to incorporate data from these patients into the analysis the importance to each endpoint of being able to identify a PR and/or to determine the occurrence and timing of progression needs to be taken into account.

For ORR it is recommended that the main (ITT) analysis includes data from patients with only non-measurable disease at baseline, handling patients with a best response of CR as “responders” with respect to ORR and all other patients as “non-responders”.

For PFS, it is again recommended that the main ITT analyses on these endpoints include all patients with only non-measurable disease at baseline, with possible sensitivity analyses which exclude these particular patients. Endpoints such as PFS which are reliant on the determination and/or timing of progression can incorporate data from patients with only nonmeasurable disease.

13.3.26 Sensitivity analyses

This section outlines the possible event and censoring dates for progression, as well as addresses the issues of missing tumor assessments during the study. For instance, if one or more assessment visits are missed prior to the progression event, to what date should the progression event be assigned? And should progression event be ignored if it occurred after a long period of a patient being lost to follow-up? It is important that the protocol and SAP specify the primary analysis in detail with respect to the definition of event and censoring dates and also include a description of one or more sensitivity analyses to be performed.

Based on definitions outlined in Section 13.3.24, and using the draft FDA guideline on endpoints (Clinical Trial Endpoints for the Approval of Cancer Drugs and Biologics April 2005) as a reference, the following analyses can be considered:

Table 16: Options for event dates used in PFS, TTP, duration of response

Situation		Options for end-date (progression or censoring) ¹ (1) = default unless specified differently in the protocol or SAP	Outcome
A	No baseline assessment	(1) Date of randomization/start of treatment ³	Censored
B	Progression at or before next scheduled assessment	(1) Date of progression (2) Date of next scheduled assessment ²	Progressed Progressed
C1	Progression or death after exactly one missing assessment	(1) Date of progression (or death) (2) Date of next scheduled assessment ²	Progressed Progressed
C2	Progression or death after two or more missing assessments	(1) Date of last adequate assessment ² (2) Date of next scheduled assessment ² (3) Date of progression (or death)	Censored Progressed Progressed
D	No progression	(1) Date of last adequate assessment	Censored
E	Treatment discontinuation due to 'Disease progression' without documented progression, i.e. clinical progression based on investigator claim	(1) N/A (2) Date of discontinuation (visit date at which clinical progression was determined)	Ignored Progressed
F	New anticancer therapy given	(1) Date of last adequate assessment (2) Date of secondary anti-cancer therapy (3) Date of secondary anti-cancer therapy(4) N/A	Censored Censored Event Ignored
G	Deaths due to reason other than deterioration of 'Study indication'	(1) Date of last adequate assessment	Censored (only TTP and duration of response)

¹.=Definitions can be found in Section 13.3.24
².=After the last adequate tumor assessment. "Date of next scheduled assessment" is defined in Section 14.1.25. ³.=The rare exception to this is if the patient dies no later than the time of the second scheduled assessment as defined in the protocol in which case this is a PFS event at the date of death.

The primary analysis and the sensitivity analyses must be specified in the protocol. Clearly define if and why options (1) are not used for situations C, E and (if applicable) F.

Situations C (C1 and C2): Progression or death after one or more missing assessments: The primary analysis is usually using options (1) for situations C1 and C2, i.e.

- (C1) taking the actual progression or death date, in the case of only one missing assessment.
- (C2) censoring at the date of the last adequate assessment, in the case of two or more consecutive missing assessments.

In the case of two or missing assessments (situation C2), option (3) may be considered jointly with option (1) in situation C1 as sensitivity analysis. A variant of this sensitivity analysis consists of backdating the date of event to the next scheduled assessment as proposed with option (2) in situations C1 and C2.

Situation E: Treatment discontinuation due to ‘Disease progression’ without documented progression: By default, option (1) is used for situation E as patients without documented PD should be followed for progression after discontinuation of treatment. However, option (2) may be used as sensitivity analysis. If progression is claimed based on clinical deterioration instead of tumor assessment by e.g. CT-scan, option (2) may be used for indications with high early progression rate or difficulties to assess the tumor due to clinical deterioration.

Situation F: New cancer therapy given: the handling of this situation must be specified in detail in the protocol. However, option (1), i.e. censoring at last adequate assessment may be used as a default in this case.

Additional suggestions for sensitivity analyses

Other suggestions for additional sensitivity analyses may include analyses to check for potential bias in follow-up schedules for tumor assessments, e.g. by assigning the dates for censoring and events only at scheduled visit dates. The latter could be handled by replacing in Table 16 the “Date of last adequate assessment” by the “Date of previous scheduled assessment (from baseline)”, with the following definition:

- **Date of previous scheduled assessment (from baseline)** is the date when a tumor assessment would have taken place, if the protocol assessment scheme was strictly followed from baseline, immediately before or on the date of the last adequate tumor assessment.

In addition, analyses could be repeated using the Investigators’ assessments of response rather than the calculated response. The need for these types of sensitivity analyses will depend on the individual requirements for the specific study and disease area and have to be specified in the protocol or SAP documentation.

13.3.27 Data handling and programming rules

The following section should be used as guidance for development of the protocol, data handling procedures or programming requirements (e.g. on incomplete dates).

13.3.28 Study/project specific decisions

For each study (or project) various issues need to be addressed and specified in the protocol or SAP documentation. Any deviations from protocol must be discussed and defined at the latest in the SAP documentation.

The proposed primary analysis and potential sensitivity analyses should be discussed and agreed with the health authorities and documented in the protocol (or at the latest in the SAP documentation before database lock).

13.3.29 End of treatment phase completion

Patients **may** voluntarily withdraw from the study treatment or may be taken off the study treatment at the discretion of the investigator at any time. For patients who are lost to followup, the investigator or designee should show "due diligence" by documenting in the source documents steps taken to contact the patient, e.g., dates of telephone calls, registered letters, etc.

The end of treatment visit and its associated assessments should occur within 7 days of the last study treatment.

Patients may discontinue study treatment for any of the following reasons:

- Adverse event(s)
- Lost to follow-up
- Physician decision
- Pregnancy
- Protocol deviation
- Technical problems
- Subject/guardian decision
- Death
- Progressive disease
- Study terminated by the sponsor
- Non-compliant with study treatment
- No longer requires treatment
- Treatment duration completed as per protocol (optional, to be used if only a fixed number of cycles is given)

13.3.30 End of post-treatment follow-up (study phase completion)

End of post-treatment follow-up visit will be completed after discontinuation of study treatment and post-treatment evaluations but prior to collecting survival follow-up.

Patients may provide study phase completion information for one of the following reasons:

- Adverse event
- Lost to follow-up
- Physician decision
- Pregnancy
- Protocol deviation
- Technical problems
- Subject/guardian decision
- Death
- New therapy for study indication
- Progressive disease
- Study terminated by the sponsor

13.3.31 Medical validation of programmed overall lesion response

As RECIST is very strict regarding measurement methods (i.e. any assessment with more or less sensitive method than the one used to assess the lesion at baseline is considered UNK) and not available evaluations (i.e. if any target or non-target lesion was not evaluated the whole overall lesion response is UNK unless remaining lesions qualified for PD), these UNK assessments may be re-evaluated by clinicians at QED Therapeutics or external experts. In addition, data review reports will be available to identify assessments for which the investigators' or central reader's opinion does not match the programmed calculated response based on RECIST criteria. This may be queried for clarification. However, the investigator or central reader's response assessment will never be overruled.

If QED Therapeutics elect to invalidate an overall lesion response as evaluated by the investigator or central reader upon internal or external review of the data, the calculated overall lesion response at that specific assessment is to be kept in a dataset. This must be clearly documented in the SAP documentation and agreed before database lock. This dataset should be created and stored as part of the 'raw' data.

Any discontinuation due to 'Disease progression' without documentation of progression by RECIST criteria should be carefully reviewed. Only patients with documented deterioration of symptoms indicative of progression of disease should have this reason for discontinuation of treatment or study evaluation.

13.3.32 Programming rules

The following should be used for programming of efficacy results:

13.3.33 Calculation of 'time to event' variables

Time to event = end date - start date + 1 (in days)

When no post-baseline tumor assessments are available, the date of randomization/start of treatment will be used as end date (duration = 1 day) when time is to be censored at last tumor assessment, i.e. time to event variables can never be negative.

13.3.34 Incomplete assessment dates

All investigation dates (e.g. X-ray, CT scan) must be completed with day, month and year.

If one or more investigation dates are incomplete but other investigation dates are available, this/these incomplete date(s) are not considered for calculation of the assessment date (and assessment date is calculated as outlined in Section 13.3.24). If all measurement dates have no day recorded, the 1st of the month is used.

If the month is not completed, for any of the investigations, the respective assessment will be considered to be at the date which is exactly between previous and following assessment. If a previous and following assessment is not available, this assessment will not be used for any calculation.

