7.1.6 Follow-up period

Patients lost to follow-up should be recorded as such on the eCRF. For patients who are lost to follow-up, the Investigator should show "due diligence" by documenting in the source documents steps taken to contact the patient, e.g. dates of telephone calls, registered letters, etc.

30-day safety follow-up period

All patients must complete the safety follow-up assessments 30 days after the last dose of the study treatment. Information relating to antineoplastic therapies taken since discontinuation of study treatment and AEs (including concomitant medication taken for ongoing AEs) will be collected for 30 days after the last dose of the study treatment.

All AEs suspected to be related to study drug should be followed up weekly, or as clinically indicated, until resolution or stability.

Disease progression follow-up period

All patients enrolled in the study who discontinue study treatment for any reason other than disease progression will have a tumor assessment every 8 weeks (\pm 7 days), until disease progression or the initiation of subsequent anticancer therapies, or death, whichever occurs first. Any newly started antineoplastic therapies during the follow-up period must be recorded on the Antineoplastic therapy since discontinuation eCRF.

Survival follow-up period

All patients enrolled in the study will be followed for survival every 4 months for one year after discontinuation of treatment. Survival follow-up will continue until all patients have discontinued study and at least 80% of the patients have died, withdrawn consent, or been lost to follow-up.

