7.2 Assessment types

7.2.1 Efficacy assessment

Tumor response will be evaluated locally by the investigator according to the guideline (see Appendix 3) based on the Response Evaluation Criteria in Solid Tumors (RECIST) Version 1.1 (Eisenhauer et al 2009). Each patient will be evaluated for all potential sites of tumor lesions at screening/baseline and every 8 weeks after starting study treatment until disease progression.

CT (Computed Tomography) /MRI (Magnetic Resonance Imaging) scans will be performed at baseline within 28 days before start of treatment and subsequently every 8 weeks from treatment start until progression of disease.

After baseline, the first assessment should be performed at Cycle 3 Day 1 (+7 day window) and all subsequent assessments should be performed within ± 7 days of the scheduled day of assessment. The same method of assessment and the same technique should be used to characterize each individual and reported lesion at baseline and during follow-up. If a patient discontinues treatment for reasons other than radiological documentation of progression of disease, an efficacy assessment should be performed at the time of End of Treatment unless a CT/MRI for tumor measurement was performed ≤ 4 weeks earlier.

Chest, abdomen, and pelvis CT scans are required for all patients at baseline. If at baseline, a patient is known to have a contraindication to CT i.v. contrast media or develops a contraindication during the trial, a contrast-enhanced MRI (if possible) of chest, abdomen, and pelvis should be performed.

For the patients with skeletal lesions suspected at baseline, a whole-body bone scan (e.g. TC 99, NaF PET, etc.) should be performed. Skeletal lesions which are identified on a whole body bone scan at baseline, which are not visible on the chest, abdomen or pelvis CT/MRI scan, should be re-imaged at baseline with localized CT, MRI or x-ray, and followed at scheduled visits (every 8 weeks).

Partial Response (PR) and Complete Response (CR) should be confirmed by repeat assessments performed at least 4 weeks and no later than 6 weeks after the criteria for response are first met.

PET/CT may be used only if it is of similar diagnostic quality as a CT performed without PET, including the utilization of oral and intravenous contrast media. While FDG-PET may complement CT scans in assessing progression per RECIST 1.1 (Appendix 3) FDG-PET assessments should be disregarded for this protocol.

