If possible, a single radiologist should perform all tumor response evaluations for an individual patient.

Any lesion that has been previously treated with radiotherapy should be considered as a nontarget lesion. However, if a lesion previously treated with radiotherapy has clearly progressed since the radiotherapy, it can be considered as a target lesion.

All radiological assessments obtained for patients enrolled during the study will be sent to The Ohio State University Multi-Site Clinical Trial Team.

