10.4.2 Secondary efficacy endpoints

Overall survival

Overall Survival (OS) is defined as the time from the date of start of treatment to the date of death due to any cause. The survival time for patients without documentation of death prior to the data cutoff, will be censored at the last date the patient was known to be alive prior to the cutoff date. Survival time for patients with no post-baseline survival information will be censored at the date of start of treatment. OS will be analyzed using the Kaplan Meier method. Survival rate at 4, 6, 8, 12, 18 and 24 months and median OS will be estimated along with 95% confidence intervals from the Kaplan Meier distribution. The FAS will be used.

Progression Free Survival

Progression free survival (PFS) is defined as the date of the start of treatment to the date of the event defined as the first documented progression or death due to any cause. If patient has not had an event, progression-free-survival is censored at the date of last adequate tumor assessment. Kaplan-Meier analysis of PFS will be conducted for each cohort.

Best Overall Response and Disease Control Rate.

Overall lesion assessments will be listed by patient. Best overall response (BOR) will be summarized for the each cohorts using the Overall Response Rate and the Disease Control Rate which are the proportion of patients having respectively a best overall response of PR or CR, or SD, PR or CR. The estimated ORR and corresponding 90% confidence intervals based on the binomial distribution will be reported.

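### Section 13.3.34 can drop a progression scan whose month is missing, or leave it undated, which biases PFS upward in the rare cases where it applies

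*Combined protocol and SAP*

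**What the plan says.** Section 13.3.34 opens by requiring complete dates: "All investigation dates (e.g. X-ray, CT scan) must be completed with day, month and year". Its second paragraph provides a fallback within one assessment: "If one or more investigation dates are incomplete but other investigation dates are available, this/these incomplete date(s) are not considered". If only the days are missing, the 1st of the month is used.

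The third paragraph covers a missing month: "the respective assessment will be considered to be at the date which is exactly between previous and following assessment". It ends: "If a previous and following assessment is not available, this assessment will not be used for any calculation".

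Three other provisions matter.

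- **When scanning stops.** Section 7.2.1 schedules imaging at baseline and "subsequently every 8 weeks from treatment start until progression of disease". For patients off treatment without progression, Section 7.1.6 continues scans "until disease progression or the initiation of subsequent anticancer therapies, or death, whichever occurs first".
- **Censoring.** Section 10.4.2 says: "If patient has not had an event, progression-free-survival is censored at the date of last adequate tumor assessment". Section 13.3.24 counts only CR, PR or SD assessments as adequate and falls back to the start of treatment if there are none after baseline.
- **Where the images go.** Section 7.2.1 says: "All radiological assessments obtained for patients enrolled during the study will be sent to The Ohio State University Multi-Site Clinical Trial Team". Section 7.3 also sends imaging to the central reader.

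**The concern.** A date-handling rule should not depend on the outcome. This one does in practice. An interim SD or PR scan has a scan on each side and gets a midpoint. A progression scan usually has nothing after it, so no midpoint exists and the literal rule discards it. The loss falls mainly on PFS events and turns them into censored times.

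The exclusion covers every calculation, so it also reaches best overall response. Section 13.3.17 requires two determinations at least 4 weeks apart for a confirmed CR or PR. If the confirming scan is the last one and lacks a month, the response could disappear from ORR.

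The section is unclear in two further ways. The condition for discarding may mean that either neighbour is absent or that both are. And the second paragraph ignores an incomplete date when another exists, while the third is triggered by a missing month on any investigation. A progression visit with a dated CT and an undated X-ray is kept under one paragraph and may be dropped under the other. Two programmers could report different event counts from the same data.

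**Working it through.** The plan states no PFS event count, power or frequency of incomplete dates, so there is no figure to reproduce. The check traces the rule and then sizes it under stated assumptions.

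**1. Worked example.** Time = end date − start date + 1 (13.3.33). Take scans on days 57 and 113 without progression, then progression on day 113 + 56 = 169 with the month missing and no other usable date.

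- Date recovered: event at 169 days.
- Literal rule: progression dropped, censored at 113 days.
- If progression is on the first scan: censored at start of treatment, duration 1 day.
- If the rule discards only when both neighbours are absent: progression kept, but the midpoint is undefined.

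**2. Do the Table 16 defaults restore the event?** Situation E (discontinuation for progression that is not documented) is ignored. Situation F (new anticancer therapy) censors at the last adequate assessment. Situation C2 (death after two or more missing assessments) censors. Only C1, death after exactly one missing assessment, still gives an event, at the later date of death.

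**3. Effect on PFS for an assumed share m of progression assessments dropped.** Assumptions: exponential PFS with median 5.8 months (borrowed from the cholangiocarcinoma study in 1.2.1.4.2, although Cohort 1 excludes that tumour), scans every 8 weeks, 24 months of follow-up, dropped patients censored at the previous scan.

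| m (assumed) | Expected events per 30 | KM PFS, 6 months | KM PFS, 12 months |
|---|---|---|---|
| 0 | 28.3 | 0.515 | 0.267 |
| 2% | 27.7 | 0.521 | 0.274 |
| 5% | 26.9 | 0.531 | 0.283 |
| 10% | 25.5 | 0.547 | 0.300 |
| 20% | 22.7 | 0.582 | 0.338 |

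The large-sample median stays on the same scan date (7.36 months) throughout, because it can move only in 8-week steps.

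**4. Effect once a deletion has occurred in a small cohort.** Same model, 3,000 simulated cohorts:

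- 1 of 30 dropped: mean KM median 6.6 to about 6.9 months; median unchanged in roughly 85% of runs.
- 2 of 30 dropped: 6.6 to about 7.2 months.
- 1 of 10 dropped: 6.4 to about 7.3 months.

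**5. How often.** If 0.5% to 2% of investigation dates lack a month (assumed) and an assessment has 1 to 4 investigations, the expected number affected among 25 progression assessments runs from 25 × 0.005 = 0.1 to 25 × (1 − 0.98⁴) = 1.9. The upper figure requires that a single undated investigation triggers the rule.

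**6. Reach into ORR.** In Cohort 1, 4 responders of 30 meets the success criterion (10.1). P(exactly 4 of 30 | ORR 25%) = C(30,4) × 0.25⁴ × 0.75²⁶ = 0.060. The loss also needs a missing month on one of the four confirming scans. With one investigation per visit and no later scan to confirm, the joint probability is 0.0604 × (1 − 0.995⁴) = 0.12% to 0.0604 × (1 − 0.98⁴) = 0.47%. With four investigations and the single-undated trigger it is 0.5% to 1.7%.

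**7. Day-only rule.** If the confirming scan has month and year only, the true interval is uniform on 28 to 42 days, and the day of the month is uniform on 1 to 30, then imputing the 1st leaves an interval of at least 28 days in 120 of 450 combinations (27%). This is conditional on that scan being month-only and ignores any later confirming scan.

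**The case against.** The strongest reply is that the trigger hardly ever fires. Section 13.3.34 itself demands full dates, 13.3.9 asks for the actual scan date for every lesion, 9.3 provides automatic checks and 9.4 sends queries for missing values. Section 13.3.27 calls these rules guidance, and PFS is a secondary endpoint with no test. This stands as an argument about frequency. It does not excuse a fallback that discards events; a fallback matters only when the controls have failed, and 13.3.32 says these rules should be used to program efficacy results.

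A reader might infer more than the documents support:

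- **That the scan lost is always the progression scan.** A last scan can be SD, PR or CR when follow-up ends at new therapy, death, withdrawal, loss to follow-up or data cut-off, and 13.3.17 foresees assessments after progression. The right word is usually.
- **That every scan date is already held centrally.** Sections 7.2.1 and 7.3 say that assessments and imaging are sent. That dates can be read from them is a fair inference, but superficial lesions may be measured by clinical examination (13.3.6), with no image behind the date.
- **That the event is certainly lost.** A prompt death can still count.
- **That the Cohort 1 verdict is at real risk.** The 6.0% and 27% are conditional on a rare trigger. A later 8-weekly scan may also confirm the response, and 10.4.1 counts any PR or CR, which leaves open whether ORR depends on confirmation at all.

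**Conclusion.** The point holds in a limited form. On its literal reading, 13.3.34 drops a progression assessment that lacks a month and has no later scan; on the alternative reading it leaves that assessment undated. The literal reading errs in one direction, towards longer PFS, and the Table 16 defaults mostly do not correct it. A final confirming scan is exposed to the same rule.

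The expected effect is small: 0.006 on 6-month PFS if 2% of progression assessments are dropped. It becomes visible only if a deletion actually occurs, and most of all in the cohorts of 10. These sizes rest on an assumed frequency, an exponential model and a median borrowed from another tumour type. The documents do not support any claim that the trial's conclusion is likely to change. The wording should still be corrected, because the rule depends on outcome, is open to two readings, and is cheap to repair.

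**What to change.** Rewrite 13.3.34 so that:

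1. An incomplete date is first recovered by site query, or from the image or radiology report sent to the lead site or central reader.
2. If any investigation at that assessment is fully dated, only the complete dates are used. This settles the conflict between the second and third paragraphs.
3. An assessment is never deleted because its date cannot be recovered. A progression stays an event. Its imputed date falls after the previous assessment, at the scheduled day where one exists, and no later than the earliest applicable of the EOT visit (for scans taken up to that visit), new anticancer therapy, death, last contact or data cut-off. An EOT scan has no 8-weekly scheduled day, so the bounds must stand on their own.
4. An undated CR, PR or SD is kept with a date imputed within the same bounds. Any response whose 4-week confirmation rests on an imputed date is flagged, including day-only imputation to the 1st.
5. PFS, and any flagged response, is re-analysed with imputed dates at their earliest and latest possible values.

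The cost is appendix wording, a little extra programming and some data queries. No new patient procedure is needed.
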